13.1 Overview

This is a single center, open label study to assess the immune responses of the Zoster Vaccine Recombinant, Adjuvanted, in different age cohorts of older adults using a systems biology approach. A total of N=60 subjects will be recruited to receive 2 doses of Zoster vaccine recombinant, adjuvanted, separated by 60 days. 30 subjects are between the ages of 50-60 years, and 30 subjects are in the age group of 70 years and above.

13.2 Endpoints

Primary Endpoint

- Differences in innate immune signatures between D0, D1, and D7 and each dose of Zoster vaccine recombinant, adjuvanted, in both age cohorts.

Secondary Endpoint

- Differences in related adverse events and serious adverse events between each dose of Zoster vaccine recombinant, adjuvanted, in both age cohorts.

Exploratory Endpoints

- The changes in transcriptomics, metabolomics and immune cell populations between D0 (before vaccination) and D1, D3, D7, D14 and D30 after each dose of Zoster vaccine recombinant, adjuvanted, in both age groups
- The changes in the phenotype of T cell responses and the kinetics of these changes between D0 (before vaccination) and D7, D14 and D30 after each dose of Zoster vaccine recombinant, adjuvanted, as well as D180 and D270+ (optional visit) in both age groups.
- The changes in the magnitude of activated B cells, antibody secreting cells and memory B cells and the kinetics of these changes between D0 (before vaccination) and D7, D14 and D30 after each dose of Zoster vaccine recombinant, adjuvanted, as well as D180 and D270+ (optional visit) in both age groups.
- The changes in VZV serology between D0 (before vaccination) and D14 and D30 after each dose of Zoster vaccine recombinant, adjuvanted, as well as D180 and D270+ (optional visit) in both age groups.
- The changes in specificity, magnitude and phenotype of VZV-specific (gE and other antigens) T cells and the kinetics of these changes between D0 (before vaccination) and 7, 14, 30 days after each dose of Zoster vaccine recombinant, adjuvanted, and at D180 and D270+ (optional visit) in both age groups.
- The changes in magnitude of VZV-specific B cells and the kinetics of these changes between D0 (before vaccination) and 7, 14, 30 days after each dose of Zoster vaccine recombinant, adjuvanted, and at D180 and D270+ (optional visit) in both age groups.
- Baseline stool microbiome alpha and beta diversity parameters.

13.3 Measures to Minimize Bias

This is an open-label mechanistic study. No randomization will be conducted.

13.4 Analysis Plan

Data from the study will be analyzed using the statistical software R. High-throughput data will be analyzed using appropriate methods, either by stand-alone software or modules in leading statistical software, e.g. the Bioconductor in the R framework. For cytokine data, missing values will be dealt with using multiple imputations. For gene expression and metabolomics data, nearest neighbor method and local least squares may be used to fill missing values. Unsupervised learning techniques such as PCA, PLSDA, clustering, and factor analysis will be used for the visualization and identification of global patterns. For descriptive endpoints, we will generate summary statistics, and visualize the data using histograms and boxplots when applicable. For the identification of innate signatures, the two age groups will be analyzed separately.

13.4.1 Analysis Populations

We will use all subjects who receive at least the first dose of the vaccine, and have measurements at days 0 and day 30 after the vaccination in the data analysis.

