8.5. Unscheduled Visits

If concerns arise between regularly scheduled visits, participants should be instructed to contact study personnel and may be asked to return to the study site for an “unscheduled” visit.

Subjects may also be asked to return for an unscheduled visit if phlebotomy is unsuccessful or if insufficient blood is collected at a prior visit. At this visit, study personnel may review their memory aid, review the vaccination site if within 14 days of vaccination, list of medications, and note any other AEs or SAEs since last visit. Blood may be drawn. Physical examination will be performed only if indicated, based on review of health status. Subjects may be also asked to report local and systemic AEs and any blood draw-related AEs or SAEs. These visits will last about 1 hour.

Early Termination Visit

At this visit, study personnel may review the memory aid with the subject (if within 7 days of vaccination) review the vaccination site, list of medications, and note any other AEs or SAEs since last visit. Blood may be drawn. Physical examination will be performed only if indicated, based on review of health status. Subjects will be also asked to report local and systemic AEs and any blood draw-related AEs. These visits will last about 1 hour.

Missed Vaccination Visit

Subjects that may have missed the second dose of the study vaccine due to the COVID-19 pandemic, may be asked to return for missed vaccination visit, if they have not received the second dose from an outside source. Subjects that agree to return will be reconsented. During the missed vaccination visit the same procedures and assessments will be followed as outlined for the second vaccination visit at Day 60. Following the second vaccination the subject will return for regular follow up visits scheduled within the specified time limits.

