8.6. Visit Windows

Study visits should take place within the time limits specified below:

D0 (first dose of vaccination) D1, D3, D7 (+/-1), D14 (+/-2), D30 (+/-7), D60 (+7) (second dose of vaccine), D61, D63, D67 (+/-1 from second vaccination), D74 (+/-2 from second vaccination), D90 (+/-7 from second vaccination), D180 (+/-14 from first vaccination, for each scheduled visit. An optional visit at any time point past 9 months (D270 +) from first vaccination may also take place.

This is also indicated on the Table of Events.

9. Mechanistic Assays

1. Expression of cytokines and chemokines via FACS. This assay will detect the expression profile of cytokines and chemokines to determine the innate response to vaccination.
2. Analysis of innate immune responses using FACS to assess numbers of activated innate cell populations. This assay will detect innate cell population activation including DC subsets, monocyte subsets, and NK cells, since these cell subsets are known to play crucial roles in immune regulation.
3. Molecular signatures of vaccination using RNA-seq on 2 mL of whole blood. This assay will determine the changes in mRNA and miRNA expression in whole blood. Results will be interpreted with use the method Significance Analysis of Microarrays (SAM) to determine change over baseline.
4. Microbiome Analysis: Analysis of microbiome diversity in the stool samples will be performed by Illumina MiSeq V4 16S Sequencing. Sample preparation will involve quantification and normalization of genomic DNA, PCR amplification of V4 hypervariable region of the bacterial 16S rDNA gene, PCR product quantification and library construction. Illumina MiSeq V4 16S sequencing and Bioinformatics analysis will involve V4 hypervariable region paired-end amplicon sequencing (MiSeq: 2x250 cycles). Filtering and trimming of all sequencing data will be done and mapped to taxonomic databases to identify bacterial composition in samples.
5. Levels of VZV-specific IgG/IgA/IgM antibody titers in the plasma by ELISA. This antibody assay will be used to quantify the levels of VZV-specific IgG and IgA in the plasma. Positive results will be assessed by 2X the negative control wells.
6. Number of VZV-specific IgG/IgA/IgM plasmablasts via ELISPOT. This cellular assay will be used to quantify the number of VZV-specific and total IgG/IgA/IgM antibody secreting cells in the blood. Positive results will be assessed by > 5 spots per million PBMCs.

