11.1. Participant Completion

Efforts are made to encourage participants to attend all clinic visits. To achieve the primary end points of the study, we will need to have longitudinal data on participants who should be able to complete, within the required windows, at least the following visits: D1, D3 and D30 after vaccination. The minimum amount of blood needed on the critical visits stated above to fulfill the primary endpoints is: 1 CPT tube.

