13.4.2 Primary Analysis of Primary Endpoint

We will use paired t-test or Wilcoxon signed-rank test to compare each immune parameter (innate immune responses) between D1 and D7 after first dose of vaccine, between D61 and D67 after second dose of vaccine, and D0 and D60 (at each dose of Zoster vaccine). The choice of the test will depend on the normality of the data, as judged by normal Q-Q plots.

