13.4.5 Analyses of Exploratory Endpoint(s)/Outcome(s)

Exploratory Endpoint 1. The innate immune response signatures are identified from traditional immune parameters, gene expression measured by RNA-seq experiment, and metabolomics data measured by LC/MS. The innate signatures will be identified for the two age groups separately. The traditional immune parameters, genes, and metabolites that change significantly over baseline after immunization are considered innate signatures.

Traditional markers will be tested using paired t-test or Wilcoxon test against D0, and significant markers will be considered part of the innate immune signature.

RNA-seq data will be preprocessed using Bowtie and Tophat, and FPKM (fragments per kilobase of exon model per million mapped reads) values will be calculated. Gene level comparison of D1, D4, D14 and D30 vs D0 will be conducted using DESeq to find the transcriptomics signature of vaccination.

Metabolomics data will be processed using packages apLCMS, XCMS, and xMSAnalyzer and generate data tables containing accurate mass m/z , retention time(s), intensity, coefficient of variation, and

related descriptive characteristics, including minimal information standards for metabolomics data. SAM(8) and similar methods will be used to detect differential abundance of features between D1, D4, D14 and D30 vs D0 to select metabolic innate signatures.

After each vaccination, the innate signatures that are correlated with the D30 antibody titers are considered correlation signatures of the innate immune responses. The correlation will be assessed using Spearman's correlation and the associated p-values.

Exploratory Endpoint 2. We will use paired t-test or Wilcoxon test to compare each immune parameter (changes in phenotype of T cell responses and the kinetics of these changes) between D7, D14 and D30 after vaccination and D0 for each dose of Zoster vaccine.

Exploratory Endpoint 3. We will use paired t-test or Wilcoxon test to compare each immune parameter (changes in the magnitude of activated B cells, antibody secreting cells and memory B cells and the kinetics of these changes) between D7, D14 and D30 after vaccination and D0 for each dose of Zoster vaccine.

Exploratory Endpoint 4. We will use paired t-test or Wilcoxon test to compare VZV serology between D14, D30, D180 and D270+ (optional visit) after vaccination and D0 for each dose of Zoster vaccine.

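### The only analysis population requires a D30 measurement that no primary endpoint or primary contrast uses, so it can discard complete primary pairs

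*Combined protocol and SAP*

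**What the plan says.** Section 13.4.1 gives the plan's only analysis population: "We will use all subjects who receive at least the first dose of the vaccine, and have measurements at days 0 and day 30". The rule is not limited to particular endpoints. Section 13.4.3 (supportive analyses) is marked not applicable, and no other set is defined.

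The primary endpoint in 13.2 is "Differences in innate immune signatures between D0, D1, and D7 and each dose of Zoster vaccine recombinant, adjuvanted, in both age cohorts". The primary analysis in 13.4.2 applies paired tests "between D1 and D7 after first dose of vaccine, between D61 and D67 after second dose of vaccine, and D0 and D60".

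Section 11.1 lists what is needed to reach the primary endpoints: "at least the following visits: D1, D3 and D30 after vaccination".

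On missing data, 13.4 states: "For cytokine data, missing values will be dealt with using multiple imputations". It adds that other filling methods may be used for gene expression and metabolomics data.

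D30 does have a role in the exploratory work of 13.4.5: "Gene level comparison of D1, D4, D14 and D30 vs D0 will be conducted using DESeq". It also enters the metabolite comparisons, the correlation with D30 antibody titers, and exploratory endpoints 2 to 6.

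**The concern.** A population rule should admit the people who can contribute to the analysis it governs. This one is keyed to a visit outside the primary analysis, so it can fail in two directions. It can remove participants whose primary data are complete, and it can admit participants who have no primary pair.

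The cohorts are small. Section 13.7 assumes 30 pairs per cohort and states no dropout allowance, 13.4 analyses the two age groups separately for innate signatures, and 11.3 does not replace anyone who has had a dose. Each pair discarded for an unrelated missed visit therefore comes straight out of the planned number.

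There is a secondary point. Section 13.4.4 names no population for adverse event rates. In 13.4.1, measurements most naturally means assay data. On a stricter reading, vaccinated participants who leave before D30 would also drop out of the adverse event rates.

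**Working it through.** **Step 1: visits required against visits used**

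| Section | Visits named | D30? |
|---|---|---|
| 13.4.1 population | D0, D30 | required |
| 13.2 primary endpoint | D0, D1, D7, each dose | no |
| 13.4.2 primary tests | D0, D1, D7, D60, D61, D67 | no |
| 11.1 visits for the primary endpoints | D1, D3, D30 | yes, but D7 absent |
| 13.4.5 exploratory | several, including D30 | yes |

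The sentence in 13.4.2 can be read as D1 against D7 (and D61 against D67), or as each post-dose day against its pre-dose sample. D30 appears in neither reading.

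**Step 2: two test cases**

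- Samples at D0, D1, D7, D60, D61 and D67, none at D30: every primary pair is present, yet the participant is excluded.
- Samples at D0 and D30 only: the participant is included and supplies no primary pair.

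**Step 3: reproduce the plan's power.** Inputs from 13.7: n = 30 pairs, effect size d = 0.66, two-sided alpha 0.01, stated power 80%. For a paired t-test, power = P(T > t), where t is the 0.995 quantile of the t distribution with n − 1 degrees of freedom and T is noncentral t with noncentrality d√n. The opposite tail is negligible.

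For n = 30, t = 2.756 and d√n = 0.66 × 5.477 = 3.615, giving power 79.7%. The stated 80% reproduces.

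**Step 4: pairs lost only because D30 is missing.** The numbers lost are assumptions.

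| Lost | n | t | d√n | Power at d = 0.66 | Effect detectable with 80% power |
|---|---|---|---|---|---|
| 0 | 30 | 2.756 | 3.615 | 79.7% | 0.662 |
| 1 | 29 | 2.763 | 3.554 | 77.8% | 0.675 |
| 2 | 28 | 2.771 | 3.492 | 75.8% | 0.689 |
| 3 | 27 | 2.779 | 3.429 | 73.7% | 0.703 |

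A simulation with 200,000 replicates gives 79.8%, 77.9%, 75.9% and 73.7%.

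**Step 5: the same loss as a rate.** Let exclusions per cohort follow Binomial(30, p), where p is an assumed probability that D30 alone is missing. Expected exclusions are 30p, the chance of at least one is 1 − (1 − p)^30, and power is averaged over the binomial.

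| p | Expected exclusions | At least one | Average power |
|---|---|---|---|
| 0% | 0 | 0% | 79.7% |
| 2% | 0.6 | 45.5% | 78.5% |
| 5% | 1.5 | 78.5% | 76.7% |
| 10% | 3.0 | 95.8% | 73.5% |

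**Step 6: who can be affected.** Only people who hold both samples of a contrast but lack D30 count. Those who leave the study before D30 also lack D60, D61 and D67, so for them only first-dose contrasts are at stake.

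**The case against.** The best defence is that the D30 requirement is deliberate. Section 11.1 also calls D30 critical for the primary endpoints. The study hypothesis (2.1) is that early innate signatures predict immunogenicity, and 13.4.5 tests this against D30 titers, to which a participant without D30 cannot contribute. One common cohort for all analyses is a defensible design.

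This explains where the rule may have come from, but it does not remove the mismatch. Section 11.1 adds D3 and D30, which the primary endpoint does not use, and leaves out D7, which it does. The titer correlation is labelled exploratory. The plan neither says that a common cohort was intended nor confines the rule to analyses that use D30.

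Other objections go to weight, and several stand:

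- The loss may be small or nil. Section 8.6 gives D30 a window: "D14 (+/-2), D30 (+/-7), D60 (+7) (second dose of vaccine". Under 8.5 a participant may be asked to "return for an unscheduled visit if phlebotomy is unsuccessful or if insufficient blood is collected at a prior visit".
- Admitting people without a primary pair does little harm to estimates, because without imputation a paired test ignores them. The reported population could still exceed the number of pairs.
- Day 30 in 13.4.1 most naturally follows dose 1, since the schedule calls the visit 30 days after dose 2 D90. But 13.4.5 uses D30 after each vaccination, so one clarifying word is worthwhile.
- The adverse event point depends on the less natural reading. Independent Safety Monitor review is unaffected, because 12.8.2.1 supplies a listing of all reported events.

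Imputation does not settle the matter. Section 13.4 does not say that it overrides the entry rule or covers a wholly missed visit.

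**Conclusion.** The concern holds and should be fixed. The plan's sole population depends on a visit that neither the primary endpoint nor the primary tests use, on either reading of 13.4.2.

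The size of the loss in this trial is unknown, because the documents give no D30 missing rate. Each pair lost costs about 2 percentage points of power at the planning effect size. That figure assumes a paired t-test at alpha 0.01 and otherwise complete data. The power statement in 13.7 is itself correct for 30 pairs. Any bias in adverse event rates is conditional on the stricter reading and cannot be quantified.

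**What to change.** - **13.4.1, primary:** for each primary contrast, analyse all vaccinated participants who have both samples of that contrast. This depends on first reconciling 13.4.2 with 13.2, so that the contrasts are unambiguous.
- **13.4.1, exploratory:** keep the D30 requirement only for analyses that use D30, namely the D30 comparisons and the D30-titer correlation. State which dose D30 follows.
- **13.4.1 and 13.4.4, safety:** base adverse event rates on everyone who received the dose concerned, and name that set in 13.4.4.
- **13.4:** add one sentence on whether imputation applies to a wholly missed visit.
- **11.1:** align the critical visits with the primary endpoint, including D7.

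The cost is wording in these sections plus the reconciliation of 13.4.2 with 13.2. No visits or samples are added. The small downside is that the number analysed will differ between contrasts and must be reported for each.

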6.5. Premature Discontinuation of Investigational Agent

Study therapy may be prematurely discontinued for any participant for any of the following reasons:

- Inability to obtain the subject's blood on multiple occasions.
- Subject does not meet the eligibility criteria anymore.
- Development of an anaphylactic or severe allergic reaction after administration of the first study vaccine.

Study therapy may also be prematurely discontinued for any participant if the investigator believes that the study treatment is no longer in the best interest of the participant.

7. Other Medications

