13.4.4 Analyses of Secondary and Other Endpoint(s)/Outcome(s)

AE rates in each group will be summarized using frequency tables. Between-group comparison will be conducted using Fisher's exact test.

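### The plan defines one analysis set, built on dose 1 plus D0 and D30 measurements, and no adverse-event denominator by dose, although the secondary endpoint compares doses

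*Combined protocol and SAP*

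**What the plan says.** The combined protocol and SAP defines one analysis population, in section 13.4.1: "We will use all subjects who receive at least the first dose of the vaccine", on the further condition of measurements at D0 and at D30 after vaccination. It sets no dose-2 condition, and no safety set or per-dose set appears elsewhere.

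The secondary endpoint (sections 3.3 and 13.2) is "Differences in related adverse events and serious adverse events between each dose of Zoster vaccine recombinant, adjuvanted, in both age cohorts". The whole planned analysis, in section 13.4.4, is "AE rates in each group will be summarized using frequency tables. Between-group comparison will be conducted using Fisher's exact test". It names neither a denominator nor a between-dose method.

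Adverse events are collected by dose. The memory aid covers D0 to D7 and D60 to D67 (section 8), and unsolicited events run for 30 days after each vaccination (section 12.2.1). SAEs are collected until study completion.

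The protocol foresees people with no observed second study dose:

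- Section 8.5 provides for "Subjects that may have missed the second dose of the study vaccine due to the COVID-19 pandemic", and allows that some may have had dose 2 from an outside source.
- Section 6.5 lists reasons for stopping after dose 1, including "Development of an anaphylactic or severe allergic reaction after administration of the first study vaccine".
- Section 11.3 rules out replacing anyone who has had at least one dose.

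**The concern.** A comparison between doses needs a denominator for each dose. The only set available to whoever programs the tables is tied to dose 1 and to a D30 measurement, and it is wrong for safety in two ways.

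First, on the natural reading D30 follows dose 1 and so comes before D60. A participant who attends D30 and then misses dose 2, or has it elsewhere, stays in the set. That person returns no D60 to D67 memory aid from the study. If counted in the dose-2 denominator, the person is treated as event-free.

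Second, a vaccinated participant who leaves before D30, perhaps because of a reaction, falls out of the set and takes any dose-1 events along.

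At stake is the only secondary endpoint. Section 5.1 itself reports more headache and shivering after dose 2 than after dose 1. If missed second doses differ by age, the comparison of the two cohorts is affected as well.

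**Working it through.** The plan states no adverse-event rate, denominator or dropout figure, so there is none to reproduce.

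**Inputs.** Planned size is 60, 30 per cohort (section 13.1). Illustrative rates come from section 5.1: headache 24.4% after dose 1 and 28.2% after dose 2; shivering 13.8% and 21.4%. The share q of the analysis set without an observed second dose is not given; I assume 5% to 20%, that is 3 to 12 of 60.

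**Step 1: dilution of the dose-2 rate.** If unobserved people are counted as event-free, tabulated dose-2 rate = true rate × (1 − q). For headache at q = 10%: 28.2 × 0.90 = 25.4. The difference columns subtract the undistorted dose-1 rate.

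| q | Headache, dose 2 | Difference from 24.4 | Shivering, dose 2 | Difference from 13.8 |
|---|---|---|---|---|
| 0% | 28.2 | +3.8 | 21.4 | +7.6 |
| 5% | 26.8 | +2.4 | 20.3 | +6.5 |
| 10% | 25.4 | +1.0 | 19.3 | +5.5 |
| 15% | 24.0 | −0.4 | 18.2 | +4.4 |
| 20% | 22.6 | −1.8 | 17.1 | +3.3 |

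The tabulated excess reaches zero at q = 1 − p1/p2, where p1 and p2 are the dose-1 and dose-2 rates. For headache this is 1 − 24.4/28.2 = 13.5% (about 8 of 60). For shivering it is 1 − 13.8/21.4 = 35.5% (about 21 of 60).

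**Step 2: the D30 condition acts on the dose-1 rate.** Suppose 3 of 60 leave before D30 (an assumption). Expected headache cases after dose 1 are 60 × 0.244 = 14.64.

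- If all three leavers had headache, the tabulated dose-1 rate is (14.64 − 3)/57 = 20.4%.
- If none had, it is 14.64/57 = 25.7%.

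Suppose also that 6 of the remaining 57 have no observed second dose. The dose-2 rate is tabulated as 28.2 × 51/57 = 25.2%. The dose difference is then +4.8 points in the first case and −0.5 in the second, against a true +3.8. The same dose-2 loss can go with a difference that is too large or too small.

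**Step 3: age groups.** Section 5.1 gives shivering after any dose as 26.8%. If 20% of one cohort has only dose 1, and those people have the dose-1 rate, that cohort shows 0.8 × 26.8 + 0.2 × 13.8 = 24.2%. The 2.6-point gap arises with no true age difference.

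**Step 4: scale against sampling error.** In a cohort of 30, q = 10% moves headache by 28.2 − 25.4 = 2.8 points, or 0.028 × 30 = 0.85 of a participant. The standard error of a dose difference, treating the doses as unpaired, is √(0.244 × 0.756/30 + 0.282 × 0.718/30) = 0.114, about 11 points.

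**The case against.** A reader might infer that the plan divides dose-2 events by everyone given dose 1, so that the dose-2 rate is always biased low and the dose difference with it. The documents do not support that.

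- The set is not everyone given dose 1. The D0 and D30 conditions already exclude early leavers, so dilution comes mainly from losses after D30.
- Section 13.4.4 names no denominator and does not say that an unobserved dose counts as event-free. An analyst who counted only people observed after dose 2 would have no dilution. The fault is an unspecified denominator.
- Section 13.4.5 uses D30 per dose. Read that way, section 13.4.1 would remove people without dose-2 follow-up and end the dilution. It would, however, exclude a dose-2 recipient who returned the memory aid but had no measurement 30 days later.
- The missed vaccination visit in section 8.5 is partly a remedy: those who return get the Day 60 procedures and regular follow-up. But they may be asked and must agree, so full recovery cannot be assumed.
- SAEs are collected to study end, so that half of the endpoint is less exposed.
- The section 5.1 rates are solicited symptoms in a large pooled cohort, whereas the endpoint is related events. At 30 per cohort the distortion is small beside sampling error.

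All of this limits the claim. None of it supplies the missing denominator. A neighbouring gap also stands: section 13.4.4 plans only a between-group Fisher test, while the endpoint compares two doses in the same people.

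**Conclusion.** The point holds as a gap in specification with conditional consequences. One set serves every analysis, it is not a safety set, and no denominator by dose is given for an endpoint that compares doses. Used literally, it understates the dose-2 rate of solicited and unsolicited events by the share of its members without an observed second dose, and it can understate the dose-1 rate by omitting people who left before D30. The net effect on the dose difference has no fixed sign.

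The dose-2 understatement is zero if every member is observed after dose 2 or if only observed people are counted. At an assumed 10% unobserved it is a tenth of the rate, for example 28.2% shown as 25.4%. This rests on reading D30 as 30 days after dose 1, on counting unobserved people as event-free, and on an assumed share, since the documents give none. It is worth correcting because the change is cheap, although the likely distortion is modest beside the imprecision of 30 per cohort.

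**What to change.** In sections 13.4.1 and 13.4.4, define safety denominators by dose, separate from the immunogenicity set:

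- Dose-1 tables: all who received dose 1, regardless of D30 data.
- Dose-2 tables: those who received the second study dose and were followed for adverse events after it.
- Between-dose comparison: those observed after both doses.
- Age-group comparisons: done separately for each dose, on these denominators.

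Report the number observed after each dose. List those without an observed second dose, with the reason, so that stopping after a dose-1 reaction stays visible.

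The cost is SAP wording and one listing, with no new data or visits. The dose-2 denominator becomes slightly smaller, and the between-dose comparison describes only people who had both doses observed; the listing is there to show who is left out.

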2.3. Secondary Objective

- To assess the safety of Zoster vaccine recombinant, adjuvanted.

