3.3. Secondary Endpoint(s)/Outcome(s)

- Differences in related adverse events and serious adverse events between each dose of Zoster vaccine recombinant, adjuvanted, in both age cohorts.

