12.4 Collection and Recording of Adverse Events

12.4.1 Collection Period

Adverse events will be collected from the time of vaccination until 30 days after each vaccination or after the participant prematurely withdraws (without withdrawing consent) or is withdrawn from the study. SAEs will be collected until a participant completes the study.

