12.8.2 Independent Safety Monitor (ISM) Review

12.8.2.1 Planned Reviews

The Independent Safety Monitor shall review safety data at least yearly. Data for the planned safety reviews will include, at a minimum, a listing of all reported AEs and SAEs.

The ISM will be informed of an Expedited Safety Report by the Protocol Chair and the DAIT/NIAID Medical Monitor in a timely manner.

12.8.2.2 *Ad hoc* ISM Reviews

In addition to the pre-scheduled planned safety monitoring, the ISM may be called upon by the DAIT/NIAID Medical Monitor for *ad hoc* reviews. The ISM will review event(s) that potentially impact(s) safety at the request of the Protocol Chair or DAIT/NIAID. In addition, the following events will trigger an *ad hoc* comprehensive ISM Safety Review:

A death of a participant, which is possibly or definitely related to the study vaccine (also a study hold - enrollment and vaccine dosing- rule)

The occurrence of one study vaccine-related and unexpected SAE or Grade 4 AE (also a study hold – enrollment and vaccine dosing- rule)

The occurrence of a Grade 3 or higher vaccine-related and unexpected SAE in 2 or more of the study participants

After review of the data, the ISM will make recommendations regarding study conduct and/or continuation.

13. Statistical Considerations and Analytical Plan

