13.4.6 Descriptive Analyses

The log₂ antibody titers of each group at each time point will be summarized and presented using histograms and strip charts for visual comparison. AE rates in each group will be summarized by tabulation.

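### As written, the adverse-event tables leave out dosed participants without a day 30 measurement, because the plan defines no separate safety set

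*Combined protocol and SAP*

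**What the plan says.** Section 13.4.1 is the only place that defines who is analysed. It opens with "We will use all subjects who receive at least the first dose of the vaccine" and adds, as a second condition joined by 'and', that they must "have measurements at days 0 and day 30 after the vaccination in the data analysis". It does not say which measurement counts, or whether the vaccination in question is dose 1 or each dose.

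Safety is the sole secondary objective (section 2.3): "To assess the safety of Zoster vaccine recombinant, adjuvanted". Its endpoint (section 3.3) is "Differences in related adverse events and serious adverse events between each dose of Zoster vaccine recombinant, adjuvanted, in both age cohorts". The planned analysis in section 13.4.4 is "AE rates in each group will be summarized using frequency tables", with Fisher's exact test between groups. Section 13.4.6 repeats that "AE rates in each group will be summarized by tabulation". Neither section names a population or a denominator.

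Data collection carries no day 30 condition. Section 12.4.1 says "Adverse events will be collected from the time of vaccination until 30 days after each vaccination", section 12.4.3 has events recorded whatever their relationship to the vaccine, and section 12.8.2.1 gives the ISM "a listing of all reported AEs and SAEs". Under section 11.3, a participant who withdraws after being dosed is not replaced.

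**The concern.** A safety denominator should depend on exposure. Here it depends on a measurement taken about a month later, which has no role in finding adverse events. A participant who has a reaction after dose 1 and leaves before day 30 would appear in the ISM's listing but not in the planned table. Someone who missed day 30 for an unrelated reason would be lost too, even with samples from days 1 to 14. If day 30 refers to dose 1 only, a person who missed that measurement but returned for dose 2 would be missing from the dose-2 rates as well.

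At stake is the reported answer to the secondary objective. With 30 per cohort and few events expected in any severe category, one or two exclusions can change a row of the table. The protocol's readers would see rates in a selected subset without being told so.

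**Working it through.** **1. Is there a stated figure to reproduce?** Not on this point. The plan gives no safety sample-size calculation, no expected dropout and no expected number without day 30 data. Section 13.7 covers immune parameters, gene expression and correlation only, and nothing below rests on it.

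**2. Which set governs the safety tables?** Section 13.4.1 states one set for the data analysis as a whole. Sections 13.4.4 and 13.4.6 state none. With no other definition in the document, 13.4.1 applies by default.

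**3. What does the rule do to a rate?** Let N be the number dosed, x the number of them with a given event, k the number without a day 30 measurement, and m the number of those k who had the event.

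- Rate among all dosed: x/N.
- Rate in the set as written: (x − m)/(N − k).
- The second is lower than the first when m/k > x/N, equal when m/k = x/N, and higher when m/k < x/N.

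The direction therefore depends on whether events were more or less common among those excluded. The documents give neither k nor m.

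**4. Illustration in one cohort.** N = 30 is from section 3.5; x = 3 and k = 3 are assumed. The rate among all dosed is 3/30 = 10.0%.

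| Excluded participants who had the event (m) | Table as written |
|---|---|
| 0 | 3/27 = 11.1% |
| 1 | 2/27 = 7.4% |
| 2 | 1/27 = 3.7% |
| 3 | 0/27 = 0% |

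**5. Illustration in the whole study.** N = 60; x = 3, k = 3 and m = 3 are assumed. The table as written shows 0/57, exact 95% interval 0 to 6.3%. Among all dosed it is 3/60 = 5.0%, interval 1.0 to 13.9%.

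**6. Is precision the problem?** Hardly. With no events, the two-sided 95% upper limit is 1 − 0.025^(1/n): 5.96% at n = 60, 6.27% at n = 57 and 6.60% at n = 54 (0, 3 or 6 excluded, an assumed range).

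**7. Anchor in the plan's own rates.** Section 5.1 gives grade 3 rates after dose 1 of 1.4% (headache), 1.4% (shivering), 2.3% (myalgia) and 2.4% (fatigue). At 2.4%, the expected count in 60 is 60 × 0.024 = 1.44. The chance of seeing at least one case is 1 − 0.976^n: 76.7% at n = 60, 75.0% at n = 57 and 73.1% at n = 54, if a missing day 30 is unrelated to the event. Random loss therefore changes little. Losing the one or two people who had the event would empty the row.

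**The case against.** Several points on the other side have force.

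- **Intent.** Section 11.1 ties the day 1, day 3 and day 30 visits to the primary endpoints, so 13.4.1 may have been meant for immune analyses only. That is plausible, but the text of 13.4.1 does not say it.
- **Oversight is intact.** Events are collected and recorded without a day 30 condition, reported quarterly to the Medical Monitor (section 12.8.1) and listed in full for the ISM. This stands: safety monitoring is unaffected. It does not correct the planned tables.
- **Few may be lost.** Day 30 has a window of 7 days either side (section 8.6), and an unscheduled visit can follow a failed draw (section 8.5). The word used is measurements, not blood samples, and Appendix D schedules adverse-event assessment at day 30. Someone who attended but gave no blood is therefore not clearly excluded. These points stand and limit the likely number.

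A reader might infer that safety would be assessed only in those who tolerated dose 1. The documents do not support that. Section 6.5 treats a severe allergic reaction as a reason to discontinue the vaccine, while leaving the study is governed separately by section 11.2. A participant who reacted badly but has day 0 and day 30 measurements stays in the set; one who tolerated the dose but moved away drops out.

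A reader might also infer that the rates are biased downward, or that the comparison between doses is distorted in a known direction. Neither follows. The documents give no link between reactions and missing day 30, and step 4 shows a shift either way. Someone who leaves before day 30 has no dose-2 data and would add nothing to a within-person comparison of doses under any population.

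**Conclusion.** The point holds in a limited form. Followed literally, section 13.4.1 removes from the adverse-event tables any dosed participant without a day 30 measurement, including early withdrawals caused by reactions, although their events have been collected. It is a stated rule that gives the wrong denominator for a safety summary, and nothing elsewhere in the plan overrides it.

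The exclusion can bias the rates, but its direction and size cannot be determined from the documents. With 3 events in 30 dosed and 3 participants without day 30, both assumed, the reported rate lies anywhere from 0% to 11.1% against 10.0% among all dosed. If everyone has a day 30 measurement, there is no effect. The conclusion assumes that 13.4.1 applies to safety because no other set is named. It is worth correcting before analysis, as a matter for the summary tables and not for participant oversight.

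**What to change.** Add to section 13.4.1: 'Safety set: all participants who receive at least one dose, regardless of available measurements; dose-2 rates use all who receive dose 2.' Name this set in sections 13.4.4 and 13.4.6. Limit any day 0 and day 30 requirement to the immune endpoints that need it, and state there which measurement is meant and whether day 30 counts from dose 1 or from each dose.

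If all enrolled participants are dosed, the dose-1 denominator becomes 60, or 30 per cohort. The cost is a sentence or two in the analysis plan, with no new data, visits or procedures.
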